**13. Consent Background**

**13.1 Waiver of Documentation Consent for CS PTSD Coach RCT**

**Title :** An RCT of a Primary Care-Based PTSD Intervention: Clinician-Supported PTSD Coach

**Approval Period:** Draft

**Check if VA related** Y

- a) **Describe the informed consent process. Include the following.**
- i) **Who is obtaining consent? (The person obtaining consent must be knowledgeable about the study.)**
  - ii) **When and where will consent be obtained?**
  - iii) **How much time will be devoted to consent discussion?**
  - iv) **Will these periods provide sufficient opportunity for the participant to consider whether or not to participate and sign the written consent?**
  - v) **What steps are you taking to minimize the possibility of coercion and undue influence?**
  - vi) **If consent relates to children and if you have a reason for only one parent signing, provide that rationale for IRB consideration.**

(i) Study research staff (RA or Study Coordinator) will obtain oral consent. (ii) Consent will be obtained by phone or in person at the VA Palo Alto. (iii) Consent is expected to take up to 15 minutes. (iv) This amount of time should be adequate for potential participants to consider whether or not to participate. If a potential participant needs more time, research staff will accommodate. (v) Potential participants will be informed that their decision to not participate will not affect their VA care. Research staff not involved in their ongoing care will obtain consent. (vi) NA.

- b) **What is the Procedure to assess understanding of the information contained in the consent? How will the information be provided to participants if they do not understand English or if they have a hearing impairment? See HRPP Chapter 12.2 for guidance.**

Potential participants will be required to be able to speak English. We will make accommodations for individuals who may have disabilities that would require alternative or additional modalities of communication to ensure they understand the information contained in the consent form.

- c) **What steps are you taking to determine that potential participants are competent to participate in the decision-making process? If your study may enroll adults who are unable to consent, describe (i) how you will assess the capacity to consent, (ii) what provisions will be taken if the participant regains the capacity to consent, (iii) who will be used as a legally authorized representative, and (iv) what provisions will be made for the assent of the participant.**

Participants will be referred to the study by their primary care providers who are knowledgeable about the study, including that those with gross cognitive impairment are not eligible. If gross cognitive impairment is apparent during the consent process, they will not be eligible for the study.

**Additional VA questions:**

- i) **List the people to whom you have formally delegated responsibility to obtain informed consent, and state whether they have the appropriate training to perform this activity.**

At this point, 2 individuals on the study team would be responsible for consenting participants. They are study research coordinators: [name] & [name].

- ii) **Will legally effective informed consent be obtained from the participant or the participant's legally authorized representative (LAR) or both? If LAR, is it clear who can serve as LAR?**

Yes, oral informed consent will be obtained from the participant. All participants must be able to provide consent for screening so will not be obtained from LARS.

- iii) **Will the circumstances of the consent process minimize the possibility of coercion or undue influence and provide the prospective participant or their representative sufficient opportunity to consider whether to participate?**

The informed consenting process will minimize the possibility of coercion or undue influence and will provide the prospective participant sufficient opportunity to consider whether to participate. This will be done by having only research staff consent participants (not clinician's involved in their care), providing adequate discussion and time to consider consenting, and informing prospective participants that their participation is voluntary and their decision to not participate will not affect their VA care.

- iv) **Will the circumstances of the consent process minimize the possibility of coercion or undue influence?**

Yes.

- v) **Will the information being communicated to the participant or the representative during the consent process exclude any exculpatory language through which the participant or the representative is made to waive or appear to waive the participant's legal rights, or release or appear to release the investigator, the sponsor, the institution, or its agent from liability for negligence (e.g. I give up any property rights I may have in bodily fluids or tissue samples obtained in the course of the research)?**

Yes.

**Title :** An RCT of a Primary Care-Based PTSD Intervention: Clinician-Supported PTSD Coach  
**Approval Period:** Draft

- vi) **Please confirm the following:**
- a. **A witness to the participant's signature or the participant's legally authorized representative's signature will sign and date the consent document.**
  - b. **If the sponsor or the IRB requires a witness to the consenting process in addition to the witness to the participant's signature and if the same person is needed to serve both capacities, a note to that effect is placed under the witness's signature line.**
  - c. **A copy of the signed and dated consent document will be given to the person signing the consent document.**
  - d. **The consent form is on the VA Form 10-1086.**

**Select ALL applicable regulatory criteria for a Waiver of Documentation and provide a protocol-specific justification:**

- 1) **45 CFR 46.117(c)(1)(i)., that the only record linking the participants and the research would be the consent document, and the principal risk would be potential harm resulting from a breach of confidentiality; each participant (or legally authorized representative) will be asked whether he/she wants documentation linking the participant with the research, and the participant's wishes govern.**
- 2) **45 CFR 46.117(c)(1)(ii)., that the research presents no more than minimal risk of harm to participants and involves no procedures for which written consent is normally required outside of the research context.**
- 3) **45 CFR 46.117(c)(1)(iii)., if participants or legally authorized representatives (LAR) are members of a distinct cultural group in which signing forms is not the norm, the research presents no more than minimal risk and there is an appropriate alternative mechanism for documenting that informed consent was obtained.**
- 4) **Y 21 CFR 56.109(c)(1)., presents no more than minimal risk of harm to participants and involves no procedures for which written consent is normally required outside of the research context.**

**Rationale for above selection:**

This study uses routine behavioral health assessments and interventions that are typically used in VA. The novel aspect of this study is that it combines two routine interventions (i.e., VA primary care mental health & the publicly available PTSD Coach app) into one intervention (i.e., Clinician-Supported PTSD Coach).

**13.2 Waiver of Documentation Telephone screen script 2017**

Check if VA related  Y

- a) **Describe the informed consent process. Include the following.**
  - i) **Who is obtaining consent? (The person obtaining consent must be knowledgeable about the study.)**
  - ii) **When and where will consent be obtained?**
  - iii) **How much time will be devoted to consent discussion?**
  - iv) **Will these periods provide sufficient opportunity for the participant to consider whether or not to participate and sign the written consent?**
  - v) **What steps are you taking to minimize the possibility of coercion and undue influence?**
  - vi) **If consent relates to children and if you have a reason for only one parent signing, provide that rationale for IRB consideration.**

(i) Research staff (RA or Study Coordinator) knowledgeable about the study will conduct the screen. (ii) Consent will be obtained by phone or in person at the VA Palo Alto. (iii) The phone screen is expected to take up to 10 minutes. (iv) This amount of time should be adequate for potential participants to consider whether or not to participate. If a potential participant needs more time, research staff will accommodate. (v) Potential participants will be informed that their decision to not participate will not affect their VA care. Research staff not involved in their ongoing care will obtain consent. (vi) NA

- b) **What is the Procedure to assess understanding of the information contained in the consent? How will the information be provided to participants if they do not understand English or if they have a hearing impairment? See HRPP Chapter12.2 for guidance.**

Potential participants will be required to be able to speak English. We will make accommodations for individuals who may have disabilities that would require alternative or additional modalities of communication to ensure they understand the information contained in the phone screen.

- c) **What steps are you taking to determine that potential participants are competent to participate in the**

**Title :** An RCT of a Primary Care-Based PTSD Intervention: Clinician-Supported PTSD Coach  
**Approval Period:** Draft

**decision-making process? If your study may enroll adults who are unable to consent, describe (i) how you will assess the capacity to consent, (ii) what provisions will be taken if the participant regains the capacity to consent, (iii) who will be used as a legally authorized representative, and (iv) what provisions will be made for the assent of the participant.**

Participants will be referred to the study by their primary care providers who are knowledgeable about the study, including that those with gross cognitive impairment are not eligible. If gross cognitive impairment is apparent during the phone screen, they will not be eligible for the study.

**Additional VA questions:**

**i) List the people to whom you have formally delegated responsibility to obtain informed consent, and state whether they have the appropriate training to perform this activity.**

i) At this point, 3 individuals on the study team would be responsible for phone screening. These include: The study PI: [name]; the study research coordinator: [name]; the study research assistant: TBD.

**ii) Will legally effective informed consent be obtained from the participant or the participant's legally authorized representative (LAR) or both? If LAR, is it clear who can serve as LAR?**

ii) Yes, informed consent to phone screening will be obtained from the participant. All participants must be able to provide consent for screening so will not be obtained from LARs.

**iii) Will the circumstances of the consent process minimize the possibility of coercion or undue influence and provide the prospective participant or their representative sufficient opportunity to consider whether to participate?**

iii) The phone screening process will minimize the possibility of coercion or undue influence and will provide the prospective participant sufficient opportunity to consider whether to participate. This will be done by having only research staff screen potential participants (not clinician's involved in their care), providing adequate discussion and time to consider participating, and informing prospective participants that their participation is voluntary and their decision to not participate will not affect their VA care.

**iv) Will the circumstances of the consent process minimize the possibility of coercion or undue influence?**

Yes

**v) Will the information being communicated to the participant or the representative during the consent process exclude any exculpatory language through which the participant or the representative is made to waive or appear to waive the participant's legal rights, or release or appear to release the investigator, the sponsor, the institution, or its agent from liability for negligence (e.g. I give up any property rights I may have in bodily fluids or tissue samples obtained in the course of the research)?**

Yes

**vi) Please confirm the following:**

- a. A witness to the participant's signature or the participant's legally authorized representative's signature will sign and date the consent document.
- b. If the sponsor or the IRB requires a witness to the consenting process in addition to the witness to the participant's signature and if the same person is needed to serve both capacities, a note to that effect is placed under the witness's signature line.
- c. A copy of the signed and dated consent document will be given to the person signing the consent document.
- d. The consent form is on the VA Form 10-1086.

**Select ALL applicable regulatory criteria for a Waiver of Documentation and provide a protocol-specific justification:**

- 1) 45 CFR 46.117(c)(1)(i), that the only record linking the participants and the research would be the consent document, and the principal risk would be potential harm resulting from a breach of confidentiality; each participant (or legally authorized representative) will be asked whether he/she wants documentation linking the participant with the research, and the participant's wishes govern.
- 2) 45 CFR 46.117(c)(1)(ii), that the research presents no more than minimal risk of harm to participants and involves no procedures for which written consent is normally required outside of the research context.
- 3) 45 CFR 46.117(c)(1)(iii), if participants or legally authorized representatives (LAR) are members of a distinct cultural group in which signing forms is not the norm, the research presents no more than minimal risk and there is an appropriate alternative mechanism for documenting that informed consent was obtained.

**Title :** An RCT of a Primary Care-Based PTSD Intervention: Clinician-Supported PTSD Coach  
**Approval Period:** Draft

- 4) Y **21 CFR 56.109(c)(1), presents no more than minimal risk of harm to participants and involves no procedures for which written consent is normally required outside of the research context.**

**Rationale for above selection:**

We will be telephone screening potential participants for eligibility prior to a more thorough in person assessment that will be completed following informed consent.

**14. Assent Background (less than 18 years of age)**

**15. HIPAA Background**

**15.1 Waiver of Authorization for waiver of authorization for recruitment**

**Recruitment**

- a) **Describe the protected health information (PHI) needed to conduct screening or recruitment. PHI is health information linked to HIPAA identifiers. List BOTH health information AND HIPAA identifiers. If you are using STARR, use the Data Privacy Attestation to ensure that your request will match your IRB-approved protocol.**

Patient names, postal address information, telephone numbers, PC-PTSD scores, SSNs, and mental health treatment history. The waiver will allow us to receive referrals from primary care staff for patients who may be eligible for this study. It will also allow us to facilitate these referrals by creating a list of patients who screen positive on the PC-PTSD on a monthly basis and then ask their providers if they will refer these patients to the study. Without the waiver, we would not be able to recruit the number of participants necessary to do the study. Without access to their medical information, we would not know who to recruit or have a way to contact the patients.

- b) Please Answer:  
 Y **Do you certify that the use or disclosure of protected health information involves no more than a minimal risk to the privacy of individuals?**  
 Y **Do you certify that the research could not practically be conducted with out the waiver?**  
 Y **Do you certify that you have adequate written assurances that the protected health information will not be reused or disclosed to any other person or entity, except as required by law, for authorized oversight of the research project, or for other research for which the use or disclosure of protected health information would be permitted?**  
 Y **Do you certify that the research could not practically be conducted with out access to and use of the protected health information?**

- c) **Please describe an adequate plan to protect any identifiers from improper use and disclosure.**

Identifiers will be stored on a secure VA server (vhpalmpncptsd1/Shared Research). Only research staff will have access to this information. This information is only used for recruitment purposes.

- d) **Please describe an adequate plan to destroy the identifiers at the earliest opportunity consistent with conduct of the research, unless there is a health or research justification for retaining the identifiers or such retention is otherwise required by law.**

Identifiers will be maintained through the duration of the research study and then destroyed consistent with VA policy.

**Title :** An RCT of a Primary Care-Based PTSD Intervention: Clinician-Supported PTSD Coach  
**Approval Period:** Draft

**15.2 Waiver of Authorization hipaa authorization**

- a) **Describe the Protected Health Information (PHI) needed to conduct the research. PHI is health information linked to HIPAA identifiers. List BOTH health information AND HIPAA identifiers. If you are using STRIDE, use the Data Privacy Attestation to ensure that your request will match your IRB-approved protocol.**

Information from the participants' VA administrative data will be extracted regarding date and types of mental health visits they have attended. Information about any new or existing mental health diagnoses (including alcohol or substance use conditions) will be extracted from the progress notes of these visits. Information about the nature of the mental health treatment received (e.g., psychotherapy, medications) will also be collected. The study will collect information about participants' demographic characteristics (e.g., age, race, ethnicity). Participants' voice will also be audio recorded (during each of the four sessions of Clinician-Supported PTSD Coach and during the telephone-based clinical interviews). Finally, IHI will also be collected during the study using self-report questionnaires and interviews. Finally, participants' email address and survey data will be collected using Stanford University School of Medicine's REDCap system (see 9. Risks, c).

- b) Please Answer:
  - Y **Do you certify that the use or disclosure of protected health information involves no more than a minimal risk to the privacy of individuals?**
  - Y **Do you certify that the research could not practically be conducted with out the waiver?**
  - Y **Do you certify that you have adequate written assurances that the protected health information will not be reused or disclosed to any other person or entity, except as required by law, for authorized oversight of the research project, or for other research for which the use or disclosure of protected health information would be permitted?**
  - Y **Do you certify that the research could not practically be conducted with out access to and use of the protected health information?**

- c) **Please describe an adequate plan to protect any identifiers from improper use and disclosure.**

Identifiers will be stored on a secure VA server. Only research staff will have access to this information. This information is only used for recruitment purposes.

- d) **Please describe an adequate plan to destroy the identifiers at the earliest opportunity consistent with conduct of the research, unless there is a health or research justification for retaining the identifiers or such retention is otherwise required by law.**

Identifiers will be maintained through the duration of the research study and then destroyed with VA policy.

**16. Attachments**

Attachment Name	Attached Date	Attached By	Submitted Date
VA HSR&D Grant Protocol	11/18/2015	[name]	
VA Required Questions	11/25/2015	[name]	
Study Measure Part 1	11/25/2015	[name]	
Study Measures Part 2	11/25/2015	[name]	
Recruitment Letter	11/25/2015	[name]	
Letter from Funder about DSMB	11/30/2015	[name]	
[name], [name] et al., in	11/30/2015	[name]	

**Title :** An RCT of a Primary Care-Based PTSD Intervention: Clinician-Supported PTSD Coach

**Approval Period:** Draft

press			
Modified Demographics Form	03/10/2017	[name]	
Collaborating Site IRB Approval Letter	06/20/2017	[name]	
Recruitment Letter Revised	07/17/2017	[name]	
HIPAA Waiver Request Form	09/14/2017	[name]	
VINCI Information for IRBs	09/14/2017	[name]	
KuhnRequestSSN 9-19-2017 signed	09/19/2017	[name]	
DSMB Annual Report FY16	12/08/2017	[name]	
DSMB 2017-2018	12/07/2018	[name]	
DSMB Feb-Dec 2018	11/25/2019	[name]	
Information for at-home intervention-assessment	03/27/2020	[name]	
COVID Stressors Survey	05/15/2020	[name]	
DSMB Jan-Dec 2019	11/10/2020	[name]	
DSMB Jan-Dec 2020	11/12/2021	[name]	

## Design and Methods Overview

This study is a two-site, two-arm, parallel RCT. Veterans with PTSD ( $N = 260$ ) will be recruited from VA PC clinics at Syracuse and Palo Alto. Participants will be randomized in equal proportions to receive 1) PC-MHI treatment as usual (PC-MHI TAU) or 2) CS PTSD Coach. Assessments will occur at baseline, 8 (post-treatment), 16, and 24 weeks post-baseline. Primary outcomes will be changes in PTSD severity and engagement in 2 sessions of specialty MH treatment. Thirty CS PTSD Coach participants will also complete a brief qualitative interview at post-treatment to evaluate their satisfaction with care. The study will use cutting-edge methodologies, including an innovative intervention package and objective app usage data to overcome limitations of self-report data.

**Data Collection Methodology.** The table below presents the measures that will be employed at each assessment time point. Baseline assessments will be conducted in person. Research staff will obtain informed consent and HIPAA authorization. Next self-report measures will be administered to assess inclusion criteria. Within one week of baseline (and prior to session 1 of CS PTSD Coach) participants will complete the CAPS-5 by phone with an independent assessor blind to condition. A post-treatment assessment (8 weeks) and two follow-up assessments (16 weeks and 24 weeks) will be conducted following baseline (Table 3). Follow-up assessments will be in person or by phone (based on participant preference) by local study staff, with the exception of the post-treatment CAPS-5, which will be conducted by phone by the independent assessor blind to condition. Several aspects of our assessment procedures, including options to assess by phone and brief assessment batteries, were designed to reduce participant burden and minimize drop-out.

**Table of Measures**

Measure	Construct	0 wk	8 wk	16 wk	24 wk
Blessed Orientation Memory Concentration	Cognitive Impairment	X			
Demographics & Military Background	Demo & Military Service	X			
Columbia-SSRS	Suicidal Ideation	X	X	X	X
Alcohol Use Identification Test (AUDIT)	Alcohol Use	X	X	X	X
Drug Abuse Screening Test (DAST)	Drug Abuse	X	X	X	X
Clinician Administered PTSD Scale-5 (CAPS-5)	PTSD (interview)	X	X		
VA Administrative Data	Treatment Engagement	X			X
Client Satisfaction Questionnaire (CSQ)	Treatment Satisfaction		X		
Patient Feedback Interviews	Patient Feedback		X		
Coping Self-Efficacy Scale	Coping Self-Efficacy	X	X	X	X
Patient Health Questionnaire-9 (PHQ-9)	Depression	X	X	X	X
WHO QOL-BREF	Quality of Life	X	X	X	X
PTSD Checklist-Specific-5 (PCL-5)	PTSD (self-report)	X	X	X	X

## Method of Randomization

Both sites will have separate randomization schemes to allow simultaneous randomization at each site. Participants will be randomized in equal proportions to conditions. Randomization schemes will be created in a password protected excel files and local study coordinators will be able to access these files to determine the randomization outcome for each participant.

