## Data Analysis and Statistical Considerations

**Power Analysis:** We propose randomizing 130 participants per condition (N = 260). Given this sample size, power was evaluated under a range of assumptions including a 15% loss to follow-up or 110 participants per condition (although under the ITT principle all 130 participants will be included in the analysis). Attrition in our pilot ([name], [name], Johnson et al., in press) at 8 weeks was 10%, similar to the 15% rate of a VA multi-site RCT with VA primary care patients. Attrition will be minimized by allowing intervention and follow-up sessions to be by phone and offering flexible scheduling of assessments (e.g., evening/ weekend times). The proposed sample size provides 80% power to detect a meaningful between group effect corresponding to a CAPS-5 difference of 7-15 points (or a Cohen's  $d$  of 0.4 or greater). These calculations conservatively assume a CAPS-5 SD ranging from 16-20 and a two-sided Wald test conducted with an alpha of .05. The effect size needed to detect a meaningful difference (i.e.,  $d = .4$ ) is smaller than what we found in our pilot work (i.e.,  $d = .55$ ). Equally important, this sample size provides adequate power to detect a statistical difference between conditions on percentages achieving clinically significant outcomes (i.e., can detect a 20% minimal difference, which is smaller than what our pilot data demonstrated, i.e., a 50% difference).

**Data Analysis:** The main goal of Aim 1 is to determine the effect of CS PTSD Coach on PTSD symptoms. More specifically, we will measure the impact of CS PTSD Coach on change in CAPS-5 score at 8 weeks. Mixed effects linear regression will be used to determine whether the effect of CS PTSD Coach on change in CAPS-5 score at 8 weeks is different from that of the comparison condition (i.e., PC-MHI TAU). As all participants will have a baseline score, they all will be included in the model, adhering to the ITT principle. The mixed effects model will include a subject-specific random effect to account for the correlation of CAPS-5 score within a person over time. Finally, because randomization is stratified by site, site will be included as a fixed effect in our model.

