The objective of Aim 2 is to correlate treatment arm with engagement in specialty MH care. We will evaluate the effect of the CS PTSD Coach condition on rate of attendance to at least 2 specialty MH visits post randomization (week 1 to week 24). To evaluate whether rates of attendance differ by condition, we will fit a mixed effects logistic regression model with a subject-specific random effect, an indicator for condition, and indicators for each time point. We are particularly interested in the effect of condition at 24 weeks. The parameter of interest, therefore, is the interaction term that corresponds to rate of treatment attendance at 24 weeks.

Several approaches will be used to evaluate our Exploratory Aims. To explore potential mediators (i.e., amount of app use, improvement in coping self-efficacy), we will fit 2 models for each potential mediator. One will include condition only and the second will include condition and the potential mediator. Change in the coefficient corresponding to condition after inclusion of the mediator may indicate a mechanism of action. To examine possible moderators (e.g., baseline PTSD severity), interaction terms between possible moderators and condition will be assessed. Significant interaction terms will suggest that the effect of intervention varies by

levels of the moderator. Lastly, to evaluate symptom trajectories over time, we will consider a mixed effects model of PCL scores at all time points with indicators for each follow-up visit (at 8, 16, and 24 weeks), randomization group, and an interaction between the indicators for time and condition as represented by the 3 product terms. A test evaluating all 3 product terms will address whether CS PTSD Coach affects the overall trajectory of PCL score. We will also explore if trajectories are moderated by continued PTSD Coach use and receipt of MH treatment. A similar approach proposed to test Aim 1 will be used to determine if CS PTSD Coach has broader effects, beyond PTSD symptom improvement, on depression and quality of life.

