### **Interim Analyses**

On an annual basis the PIs will compile data on enrollment, baseline and follow-up clinical data, protocol compliance, data quality, adverse events, and protocol deviations. These analyses will be conducted as follows. First, for purposes of the annual review summary to the DSMB, simple analyses will be conducted to determine the presence of issues related to recruitment, randomization, biases in attrition, or other operational problems that might affect the integrity of the study.

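### The Aim 2 model omits site, the stratification factor, and has no baseline covariate; add site and pre-randomisation PCL-5 before analysis

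*SAP*

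**What the plan says.** **Aim 1 (SAP, Data Analysis).** Change in CAPS-5 at 8 weeks is analysed by a mixed linear model. The SAP gives its reason for one covariate: "because randomization is stratified by site, site will be included as a fixed effect in our model".

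**Aim 2 (same section).** Attendance at two or more specialty visits is analysed with a "mixed effects logistic regression model with a subject-specific random effect, an indicator for condition, and indicators for each time point". The SAP then adds: "The parameter of interest, therefore, is the interaction term that corresponds to rate of treatment attendance at 24 weeks". Neither site nor any baseline variable is named.

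**Timing of baseline measures.** Protocol 2a lists the eligibility questionnaires, then randomisation, then the baseline CAPS-5 by telephone within a week. PCL-5 of 33 or more is the inclusion criterion (Protocol 8h), so the week-0 PCL-5 precedes assignment. The SAP Table of Measures repeats PCL-5 at 8, 16 and 24 weeks, and lists "VA Administrative Data" at weeks 0 and 24.

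**Allocation.** Each site has its own scheme in a password-protected spreadsheet, and "local study coordinators will be able to access these files to determine the randomization outcome for each participant" (SAP, Method of Randomization). Protocol 13.1 has a research assistant or coordinator obtain consent at Palo Alto and names two research coordinators as the people delegated. Under Interim Analyses the SAP says that "simple analyses will be conducted to determine the presence of issues related to recruitment, randomization, biases in attrition", without saying what will be examined.

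**The concern.** The SAP's reason for including site in Aim 1 applies equally to Aim 2: the same people were randomised through the same two site lists. Omitting the stratum from one of two primary models is inconsistent. If site or severity predicts attendance, the omission also gives up precision and leaves any imbalance in severity between arms uncorrected.

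The allocation arrangements add some weight. Staff who can open the list may also be staff who decide entry, and no sequence method, independent list holder or one-at-a-time release is described. If foreknowledge had influenced entry, both primary comparisons could be biased. An Aim 2 model without baseline covariates would not correct even the measurable part of that bias.

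Aim 1 has a smaller, related weakness. Its baseline value, the CAPS-5, is listed after randomisation, so PCL-5 is the severity measure that clearly precedes assignment.

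**Working it through.** **1. The two primary models side by side.**

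| Term | Aim 1 (CAPS-5 change) | Aim 2 (2+ specialty visits) |
|---|---|---|
| Condition | yes | yes |
| Subject random effect | yes | yes |
| Site | yes, because of stratification | not listed |
| Baseline severity | CAPS-5, listed after randomisation | not listed |
| Pre-randomisation PCL-5 | not listed | not listed |

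**2. The plan's own figure for a binary outcome.** The Power Analysis says that the sample size "can detect a 20% minimal difference" on the proportions with clinically significant outcomes. It gives no control rate and does not name attendance. The inputs are 110 per arm after 15% loss (130 × 0.85 = 110.5) and two-sided alpha 0.05. With p̄ the mean of the two rates:

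power = Φ{[0.20 − 1.96·√(2p̄(1−p̄)/110)] / √([p₁(1−p₁)+p₂(1−p₂)]/110)}

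| Rates | Power |
|---|---|
| 10% v 30% | 96.4% |
| 20% v 40% | 90.5% |
| 30% v 50% | 86.2% |
| 40% v 60% | 84.8% |
| 50% v 70% | 86.2% |

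The claim of adequate power is reproduced. The sample size is not in question.

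**3. What the covariates do when allocation is sound.** The documents give no attendance rate or covariate effects, so all of these are assumptions: attendance 20%, 35% or 50%; log-odds of 0.5 per SD of PCL-5, 0.5 per SD of an unmeasured trait and 0.7 for site; odds ratio 2.2 when there is an effect. The simulation had 114 v 118 people, one binary outcome each, ordinary logistic regression and 3,000 runs per scenario.

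| Attendance | Power, condition only | Power, plus site and PCL-5 | Gain (points) |
|---|---|---|---|
| 20% | 70.1% | 71.7% | 1.6 |
| 35% | 75.2% | 79.8% | 4.6 |
| 50% | 77.2% | 78.1% | 0.9 |

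The simulation error of each power is about √(0.75 × 0.25/3000) = 0.8 points, so the differences between rows should not be over-read. A separate run with assumed effects gave about 79% rising to 82%. With no true effect, type I error was 4.6–4.8% with condition only and 4.8–5.0% with both covariates. The omission therefore costs efficiency; it does not invalidate the test.

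**4. What the covariates do if the arms differ at entry.** Assume a difference of 0.4 SD between arms, no treatment effect and a nominal 5% test.

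| Imbalance in | Type I error, condition only | Plus site and PCL-5 |
|---|---|---|
| PCL-5 | 9.3–10.2% | 4.7–5.2% |
| Unmeasured trait | 7.5–10.0% | 7.7–9.8% |
| Both | 21.9–27.7% | 8.5–11.5% |

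Adjustment removes the part due to PCL-5 and nothing else. Adding site alone changed almost nothing in these rows.

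**5. How precisely baseline PCL-5 can be compared by arm.** The 95% half-width in SD units is 1.96·√(1/n₁ + 1/n₂):

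- Overall, 114 v 118: 0.26
- Syracuse, about 82 v 82: 0.31
- Palo Alto, about 35 v 35: 0.47

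The site figures halve the eligible counts (164 and 70, Continuing Review Form 1a), which assumes an equal split. The comparison can show a large imbalance in severity. It cannot prove concealment.

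**The case against.** The strongest reply is that covariate choice is largely preference. Without an imbalance the condition-only model already holds its type I error, and site alone adds almost nothing. PCL-5 is a self-report taken by research staff and is itself the entry threshold, whereas the SAP says the baseline CAPS-5 assessor is blind to condition. The Aim 2 model also has a more basic problem, since it targets an interaction that its list of terms does not contain. Much of this stands: the gain is small, the blind assessor is a real protection, and the model's form needs separate attention. None of it explains why the stratum enters one primary model and not the other.

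A reader might go further and infer that allocation was subverted. The documents do not support that:

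- The Palo Alto delegation describes the position at the time of writing, under oral consent. Continuing Review Form 2e and 2g refer to signed consent forms in earlier years, so who consented most participants is not documented. Nor is the division of roles at Syracuse.
- Protocol 16 lists the "VA HSR&D Grant Protocol" as an attachment. It was not supplied and may describe concealment.
- Of 356 enrolled, 122 were not eligible. That is expected when consent precedes eligibility testing, and no reasons are given. An unknown share may simply have scored below the PCL-5 cut-off.
- The difference between 234 eligible and 232 randomised is not an anomaly in itself. The two counts can differ, and part of the form was removed before review.

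**Conclusion.** The point holds as a gap in the Aim 2 analysis and should be fixed before the data are analysed. Site belongs in the model on the SAP's own reasoning. Baseline PCL-5 belongs there as the severity measure already collected before assignment. The expected gain is about 1 to 5 points of power, provided the covariates predict attendance roughly as assumed; if they do not, the gain will be close to nil and the cost still negligible.

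On concealment the supported conclusion is narrower: the supplied documents do not exclude foreknowledge, and they do not show it. The size of any resulting bias cannot be estimated from them. Nor should a reader take adjustment as a remedy. A preference for specialty care bears directly on Aim 2, is itself an exclusion criterion (Protocol 8h), and is not measured by PCL-5.

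**What to change.** Add one paragraph to the SAP before analysis:

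1. **Aim 2.** Include site and week-0, pre-randomisation PCL-5 as fixed covariates, whatever final form the model takes. Specify week 0 explicitly, because a later PCL-5 would adjust for a post-randomisation variable. State that the odds ratio is then conditional on these covariates.
2. **Optional Aim 2 covariate.** Add prior specialty mental health visits from the week-0 administrative data if they vary. They may vary little, since patients already in counselling are excluded.
3. **Aim 1.** Keep the planned model and add a sensitivity analysis that includes baseline PCL-5.
4. **Reporting.** Give baseline PCL-5 by arm within site, as standardised differences with 95% intervals. Cite the grant protocol on concealment if it covers the point; if concealment cannot be documented, state this as a limitation. Do not describe adjustment as correcting selection on unmeasured traits.

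All of this uses data already collected. The Continuing Review Form (items 3a and 4) reports enrolment closed, data being prepared and no interim findings, so the covariates can still be fixed before results are known. The only downside is that a limitation may have to be stated.
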